In parallel and under the same IND (#15703), a second phase I trial is being conducted with NeoVax (DF/HCC # 14-362 - A Phase I Study of a Personalized NeoAntigen Cancer Vaccine with Radiotherapy Among MGMT Unmethylated, Newly Diagnosed Glioblastoma Patients). Both trials utilize early stage patients who are otherwise healthy with competent immune systems. For both trials, the NeoVax personalized peptides are being produced by the same process and released to the same specifications, identical amounts are being used and the identical amount of Hiltonol® is added. In both trials the vaccination schedule is identical and the definition of Dose Limiting Toxicities is identical. In both trials, an initial cohort of five patients is being evaluated for safety.

For the purposes of evaluation of safety in the five patient cohort for either trial, the initial patients from both trials will be combined to achieve the required 5 patient cohort. Once 5 patients from the combined trials have successfully reached the end of the DLT evaluation window (4 weeks after the last priming dose) and if fewer than two DLTs have been observed, treatment can initiate to complete the initial 5 patient cohort and for the additional 10 patients at the selected dose.

CONFIDENTIAL

This document is confidential. Do not disclose or use except as authorized.

The primary objectives of the study are to test the safety and feasibility of administering NeoVax; the secondary objectives include evaluating the immune response to the personalized neoantigens and monitoring disease recurrence.

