5.4 Dose schema and staggering of patients

5.4.1 DLT and expansion cohorts

Five patients will be entered for the initial safety evaluation (Cohort 1). If two or more patients in Cohort 1 experience dose limiting toxicity (DLT) during the first 7 weeks of treatment, then that cohort will be determined to have unacceptable toxicity; otherwise, an additional 10 patients will be treated at the initial dose to increase the likelihood of detecting serious toxicities, to complete biologic correlative endpoints, and to gain preliminary experience with clinical tumor activity. If Cohort 1 is found to have unacceptable toxicity, then 5 patients may be enrolled on cohort -1 shown below. For Cohort -1, the dose of poly-ICLC is dropped by 50% relative to Cohort 1 but the dose of peptides remains the same. If two or more patients in Cohort -1 experience a DLT, then the study will be stopped. If none or only one patient experiences a DLT on Cohort -1, then 10 additional patients will be enrolled for additional toxicity evaluation, to complete biologic correlative endpoint, and to gain preliminary experience with clinical tumor activity. If four or more patients in the expansion cohort experience dose limiting toxicity (DLT) during the first 7 weeks of treatment, then that cohort will be determined to have unacceptable toxicity and further dosing of all patients will be stopped.

Dose De-escalation Schedule 1 cycle = 22days		
	Dose Level	Dose of poly-ICLC
	- 1	0.25 mg per injection site (4 injections, total dose 1 mg Vol = 4 x 0.875 ml)
Starting Dose →	1	0.5 mg per injection site (4 injections, total dose 2 mg)

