5.5 Definition of Dose-Limiting Toxicity

Dose-limiting toxicity (DLT) is based on the CTEP Active Version (version 4.0) of the NCI Common Terminology Criteria for Adverse Events (CTCAE). DLT refers to toxicities experienced within 49 days (7 weeks) of treatment initiation (“DLT window”). If treatment has to be delayed because of a toxicity that does not fulfill the criteria of a DLT, the DLT window should be extended by that time period of delay. A DLT will be defined as follows:

1. Grade 3 or 4 toxicity that is definitely, probably, or possibly related to the administration of vaccine, excluding:
 - Transient (\leq 72 hours) flu-like syndrome;
 - Grade 3 nausea, vomiting, constipation, or diarrhea that returns to grade 2 (or lower) level within 48 hours;
 - Grade 3 rash that resolves to grade 2 or grade 1 within \leq 14 days.
2. Grade 3 or 4 abnormal laboratory value that is definitely, probably, or possibly related to the administration of vaccine if it persists for more than 7 days, requires hospitalization or medical intervention (except for Grade 3 electrolyte abnormality that lasts \leq 72 hours, is not clinically complicated, and resolves spontaneously or responds to conventional medical intervention).
3. Any grade 3 or grade 4 toxicity that is considered, in the opinion of the investigator, to be dose-limiting.
4. Any death related to study treatment.

CONFIDENTIAL

This document is confidential. Do not disclose or use except as authorized.

Management and dose modifications associated with the above adverse events are outlined in Section 6 (Expected Toxicities and Dosing Delays/Dose Modifications).

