6.3 Dose Modifications/Delays

- 6.3.1** If a patient develops grade 3 toxicity attributable to the vaccine, additional treatment will be withheld until the toxicity has resolved or improved to grade 1. If the toxicity constitutes a DLT as defined in 5.5, the patient will be removed from the study. If the toxicity does not fulfill the criteria of a DLT, the next vaccine administration may be delayed for a maximum duration of 14 days. If vaccine dosing has to be delayed more than 2 times because of a toxicity that is not considered a DLT, the patient will be removed from the study.
- 6.3.2** If a patient develops grade 4 toxicity attributable to the vaccine (with the exception of certain grade 4 laboratory abnormalities as defined in section 5.5), he or she will be removed from treatment.
- 6.3.3** If two or more grade 4 or greater toxicities attributable to the vaccine are observed, the trial will be suspended to investigate the causes of these (unexpected) toxicities.

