14 STATISTICAL CONSIDERATIONS

14.1 Study Design/Endpoints

The primary goals of this Phase I trial are: a) to assess safety of the vaccine and determine the recommended dose of poly-ICLC and b) to assess the feasibility of making vaccine containing an adequate number of actionable peptides and in a timely manner.

A. To evaluate safety and tolerability of administering NeoVax in patients with high-risk melanoma.

Dose-limiting toxicity (DLT) will be defined as any of the following toxicities observed:

1. Grade-3 or -4 toxicity that is definitely, probably, or possibly related to the administration of vaccine, excluding:
 - Transient (\leq 72 hours) flu-like syndrome
 - Grade-3 injection site reaction (localized rash, erythema, edema, induration) that resolves to grade 2 (or lower) within 72 hours
 - Grade-3 nausea, vomiting, constipation, or diarrhea that returns to grade 2 (or lower) within 48 hours
 - Grade-3 rash that resolves to grade 2 or grade 1 within 14 days
2. Grade-3 or -4 abnormal laboratory value that is definitely, probably, or possibly related to the administration of vaccine if it persists for more than 7 days, requires hospitalization or medical intervention (except for Grade-3 electrolyte abnormality that lasts \leq 72 hours, is not clinically complicated, and resolves spontaneously or responds to conventional medical intervention)

CONFIDENTIAL

This document is confidential. Do not disclose or use except as authorized.

3. Any grade-3 or grade- 4 toxicity that is considered, in the opinion of the investigator, to be dose-limiting
4. Any death related to study treatment

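### Sections 5.5 and 14.1 define dose-limiting toxicity differently: only 14.1 excludes grade 3 injection-site reactions that settle within 72 hours

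*Combined protocol and SAP*

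**What the plan says.** Both definitions are current text. They start from the same rule: a related grade 3 or 4 toxicity counts unless excluded.

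- **Section 5.5, item 1** has three exclusions: flu-like syndrome of up to 72 hours, grade 3 gastrointestinal events that improve within 48 hours, and "Grade 3 rash that resolves to grade 2 or grade 1 within" 14 days.
- **Section 14.1, part A, item 1** has the same three, with the rash line reading "Grade-3 rash that resolves to grade 2 or grade 1 within 14 days", and adds a fourth: "Grade-3 injection site reaction (localized rash, erythema, edema, induration) that resolves to grade 2 (or lower) within 72 hours".

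Items 2 to 4 agree in substance.

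The decision rules are also given twice. Section 5.4.1, just before the 5.5 definition, declares the dose unacceptable "If two or more patients in Cohort 1 experience dose limiting toxicity (DLT) during the first 7 weeks of treatment", and sets four or more DLTs as the limit for the 10-patient expansion cohort. Section 14.1 repeats both rules after its own definition.

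Removal of a patient follows Section 6.3.1: "If the toxicity constitutes a DLT as defined in 5.5, the patient will be removed from the study". For a grade 3 toxicity that is not a DLT, "the next vaccine administration may be delayed for a maximum duration of 14 days".

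Section 1.1 says of the parallel glioblastoma trial: "In both trials the vaccination schedule is identical and the definition of Dose Limiting Toxicities is identical". On that basis, "the initial patients from both trials will be combined to achieve the required 5 patient cohort".

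**The concern.** The DLT count is the primary safety measure. It decides expansion, dose reduction or stopping, with only five patients in the first cohort. The affected events are the kind this vaccine is expected to cause: Section 6.1.1 lists erythema, induration and edema among the local reactions to poly-ICLC, and each priming visit involves injections at up to four sites.

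Under one section a brief grade 3 local reaction removes the patient; under the other it delays the next dose by at most 14 days. A patient could be removed for a DLT that the Section 14.1 count leaves out. A patient removed before the first boost is also lost to the immunologic analysis, because Section 5.4.4 requires all priming doses and the first boost.

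**Working it through.** **1. Compare the exclusions for a vaccine-related grade 3 event.**

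| Event | Section 5.5 | Section 14.1 |
|---|---|---|
| Flu-like syndrome, up to 72 h | not a DLT | not a DLT |
| Gastrointestinal, improved within 48 h | not a DLT | not a DLT |
| Rash, improved within 14 days | not a DLT | not a DLT |
| Injection-site erythema, edema or induration, improved within 72 h | **DLT** | **not a DLT** |

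Only the last row differs.

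**2. Look for a clause that reconciles them.** The rash line in 5.5 does not cover the last row, because Sections 6.1.1 and 14.1 both name localized rash separately from erythema, edema and induration. Item 3 (investigator opinion) can add a DLT but cannot excuse one. No text ranks one definition above the other for the cohort count.

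**3. Reproduce the plan's figures.** For Cohort 1 at a true DLT rate of 10%:

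P(0 or 1 of 5) = 0.9^5 + 5 × 0.1 × 0.9^4 = 0.590 + 0.328 = 0.919; the plan prints 92%.

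The other rows give 73.7, 52.8, 33.7, 18.8 and 8.7%, against 74, 53, 34, 19 and 9%. For the expansion cohort, P(4 or more of 10) at 5, 10, 20, 30, 36 and 40% is 0.001, 0.013, 0.121, 0.350, 0.513 and 0.618, as printed. Both tables are functions of the DLT rate, so making the definitions agree leaves them unchanged.

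**4. Effect on decisions, with no assumed rate.**
- Cohort 1 has one DLT under both definitions and one other patient with only a brief grade 3 local reaction. The count is 1 under 14.1 (expand) and 2 under 5.5 (reduce poly-ICLC by 50%).
- The same pattern in Cohort -1 separates expansion from stopping the study.
- In the expansion cohort, three shared DLTs plus one such patient give 3 against 4, which is continue against stop.

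**5. Illustration with assumed rates.** Assume 10% of patients have a DLT from other causes and, independently, a share q has a brief grade 3 local reaction. The DLT rate under 5.5 is p = 1 − 0.9 × (1 − q).

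| q (assumed) | p under 5.5 | P(expansion), 5.5 | P(expansion), 14.1 | Opposite Cohort 1 decisions |
|---|---|---|---|---|
| 1% | 0.109 | 90.5% | 91.9% | 1.4% |
| 2% | 0.118 | 89.1% | 91.9% | 2.8% |
| 5% | 0.145 | 84.4% | 91.9% | 7.4% |

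Every DLT under 14.1 is also one under 5.5 here, so the last column is the difference, taken before rounding.

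**6. What the documents say about frequency.** Section 6.1.1 calls earlier poly-ICLC reactions generally mild to moderate. Section 2.1.1 reports no toxicity above grade 2 in the long-peptide studies, without patient numbers. Section 2.1.2.4 reports no grade 3 or 4 events in 11 patients given poly-ICLC with NY-ESO-1 peptides. Zero of 11 gives a one-sided 95% upper bound of 1 − 0.05^(1/11) = 23.8%, too wide to narrow the range in step 5.

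**The case against.** The strongest reply is that 5.5 already governs. It is the section headed as the DLT definition, it sets the 49-day window and its extension for delays, it follows directly on the 5.4.1 rules, and 6.3.1 and 6.3.2 cite it. Nothing cites 14.1 for this purpose. That makes 5.5 the more natural operative text and the right home for a single definition. It does not remove the conflict, because 14.1 states its own definition in full and then applies the same cohort rules.

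Four stronger readings are tempting, and the documents do not support them:

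- **Section 14.1 contradicts itself on localized rash.** A reader might infer this because the rash appears under both a 72-hour and a 14-day limit. The lines are separate exclusions, and ordinarily meeting any one is enough. The 14-day line then governs, in agreement with 5.5, and the mention in the 72-hour line is redundant.
- **The printed probabilities are wrong.** They reproduce exactly.
- **Patients lose immediate protection.** Section 6.3.1 withholds vaccine after any attributable grade 3 toxicity until it has resolved or improved to grade 1, whether or not it is a DLT, and 5.5 is the stricter list.
- **Pooling with the parallel trial is invalid.** That protocol is not in the documents, so which wording it uses cannot be checked.

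It is also fair to object that the rates in step 5 have no source. They show scale only; the discrepancy stands without them.

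**Conclusion.** The inconsistency is real and confined to one kind of event: vaccine-related grade 3 erythema, edema or induration at the injection site that falls to grade 2 or lower within 72 hours. It is a DLT with removal under 5.5 and not a DLT under 14.1. One such patient can reverse the Cohort 1 decision when another patient already has a DLT. Such events are probably uncommon, and the documents give no rate, so no probability of a reversal can be stated as a finding. What is at stake is who is counted and who is removed. It should be corrected, because the count drives the trial's main safety decisions and the correction is cheap. The conclusion assumes only that the two exclusion lists are meant to be complete.

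**What to change.** Keep one definition, in Section 5.5, and replace the list in 14.1 with a reference to it. This retains the stricter list and requires no change to 6.3.1 or 6.3.2.

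If the investigators intend the injection-site exclusion, add a line to 5.5 exempting grade 3 erythema, edema or induration at the injection site that improves to grade 2 or lower within 72 hours, and still have 14.1 refer to 5.5. The downside is a slightly more lenient DLT rule, under which these patients have a dose delayed and stay on study. Item 3 remains as a backstop. The documents do not show which was intended, so the investigators should say.

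Either way, confirm that the wording matches the parallel glioblastoma protocol before pooled patients are counted. If any 72-hour line is kept, leave localized rash out of it, since the 14-day line already covers it.

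The cost is a wording amendment here and possibly a matching one in the parallel trial. Sample size and both probability tables stay as they are.

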1. OBJECTIVES

1.1 Study Design

The study is an open label, phase I trial in which patients with high-risk melanoma will be immunized with up to 20 peptides that are both specific to the patient's tumor cells (i.e. – not found in their normal cells) and unique to the patient (i.e. – “personal”). These peptides are encoded by missense mutations, in-frame gene fusions and novel open reading frame mutations (collectively known as “neoantigens”) that have occurred within that patient's tumor cells and are identified through DNA and RNA sequencing. Up to 20 peptides about 20-30 amino acids in length will be prepared for each patient and will be administered together with the immune adjuvant poly-ICLC. Thus, the personalized NeoAntigen Cancer Vaccine consists of peptides + poly-ICLC and will be termed “NeoVax”.

Eligible patients will be initially entered into the trial to undergo surgery with the intent to resect all melanoma detectable clinically and on radiographic scans. Patients will be reassessed for eligibility prior to the first vaccination and will continue onto the treatment phase of the trial if secondary eligibility criteria are met.

Five patients will be entered for the initial safety evaluation (Cohort 1). If none or only 1 patient experiences a DLT on Cohort 1, an additional 10 patients will be treated at this dose to increase the likelihood of detecting serious toxicities, to complete biologic correlative endpoints and to gain preliminary experience with clinical tumor activity. If two or more patients in Cohort 1 experience dose limiting toxicity (DLT) during the first 7 weeks of treatment, then the dose of poly-ICLC will be reduced by 50% and 5 patients will be enrolled on Cohort -1. If none or only 1 patient experiences a DLT on Cohort -1, then an additional 10 patients will be enrolled as described above. If two or more patients in Cohort -1 experience a DLT, then the study will be stopped.

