Five patients will be entered for the initial safety evaluation (Cohort 1). We have chosen dose escalation cohorts of 5 patients, rather than a more traditional 3+3 design, because the determination of whether to treat at a different dose in this trial is made over a longer period of time due to the staggered enrollment of patients, the time required for vaccine preparation, and the extended period for safety evaluation. These larger cohort sizes help us avoid having to pause and then restart enrollment to a dosing cohort several months later. If two or more patients in Cohort 1 experience dose limiting toxicity (DLT) during the first 7 weeks of treatment, then that cohort will be determined to have unacceptable toxicity; otherwise, an additional 10 patients will be treated at this dose level to increase the likelihood of detecting serious toxicities, to complete biologic correlative endpoints, and to gain preliminary experience with clinical tumor activity. If Cohort 1 is found to have unacceptable toxicity, then 5 patients will be enrolled on Cohort -1. If two or more patients in Cohort -1 experience a DLT, then the study will be stopped. If zero or one patient experiences a DLT in Cohort -1, then 10 additional patients will be enrolled in an expansion cohort.

The table below shows the probability of moving to the dose expansion phase (0 or 1 patients with DLT out of 5 patients) for various possible values of the true, but unknown, toxicity rate.

True rate of DLT (%)	Probability of Dose Expansion (%)
10	92
20	74
30	53
40	34
50	19
60	9

If the true probability of DLT is 10% or less, then the probability of proceeding to dose expansion is at least 92%. The probability of dose expansion is less than 50% if the true rate of dose-limiting toxicities is 32% or greater.

Minimum vaccination requirement to pass DLT observation period: A minimum of 3 vaccinations and absence of DLTs are required for a patient to complete the 7-week DLT observation period successfully.

Expansion Cohort: When the recommended dose has been determined, an expansion cohort of 10 patients will be enrolled to assess the performance of the vaccine and to gain additional information about toxicities.

CONFIDENTIAL

This document is confidential. Do not disclose or use except as authorized.

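### Section 1.1 opens expansion on a DLT count pooled with the glioblastoma trial, 5.4.1 and 14.1 on Cohort 1, and the text does not settle which DLT rule covers melanoma patients who complete Cohort 1 afterwards

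*Combined protocol and SAP*

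**What the plan says.** Section 1.1 first states a rule for this trial's own cohort: "If none or only 1 patient experiences a DLT on Cohort 1, an additional 10 patients will be treated at this dose". Section 5.4.1 gives the converse, with unacceptable toxicity declared under this condition: "If two or more patients in Cohort 1 experience dose limiting toxicity (DLT) during the first 7 weeks of treatment". Section 14.1 repeats that rule. Its table is headed "The table below shows the probability of moving to the dose expansion phase (0 or 1 patients with DLT out of 5 patients") and is summarised in two sentences: "If the true probability of DLT is 10% or less, then the probability of proceeding to dose expansion is at least 92"%, and "The probability of dose expansion is less than 50% if the true rate of dose-limiting toxicities is 32% or greater".

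Later in 1.1 the safety cohort is shared with the parallel glioblastoma trial: "the initial patients from both trials will be combined to achieve the required 5 patient cohort". Once five pooled patients have reached the end of the DLT window, "if fewer than two DLTs have been observed, treatment can initiate to complete the initial 5 patient cohort and for the additional 10 patients". The stated grounds for pooling include "In both trials the vaccination schedule is identical and the definition of Dose Limiting Toxicities is identical", together with the same manufacturing process and the same amounts of peptide and adjuvant.

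Neither 5.4.1 nor 14.1 mentions pooling. The stopping rule of four or more DLTs counts only the 10 expansion patients.

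**The concern.** The pooled five and this trial's first five are the same people only if every pooled patient has melanoma. Otherwise Section 1.1 expects further melanoma patients to be treated to fill Cohort 1 after the pooled gate has opened, and it lets expansion start on the same signal. For those later patients the text allows two readings:

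- The two-DLT rule in 5.4.1 and 14.1 still covers them, because they are Cohort 1 patients. Nothing then says what a second Cohort 1 DLT does once expansion patients are on treatment.
- The pooled gate has replaced that rule. They then fall under no DLT-count rule, because they are outside both the pooled five and the 10 expansion patients.

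Safety is a primary objective, and this rule decides whether 10 more patients are exposed. The pooled count can pass while Cohort 1 ends with two or more DLTs, and the plan does not say what follows.

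**Working it through.** **Inputs.** From the documents: five patients at the gate, pass on 0 or 1 DLT (1.1, 14.1), and the printed table (14.1). Assumed: k of the pooled five are melanoma patients (not given, so k = 0 to 5 is shown), all patients are independent, and both trials share one DLT rate p.

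**Step 1: the printed table.** P(0 or 1 of 5) = (1−p)^5 + 5p(1−p)^4. At p = 10/20/30/40/50/60% this gives 91.9/73.7/52.8/33.7/18.8/8.7%, against 92/74/53/34/19/9 printed. It is 48.7% at p = 32% and crosses 50% at 31.4%. The table and both summary sentences reproduce. They fit Cohort 1 alone, or the pooled five alone under a common rate.

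**Step 2: how often the two counts disagree.** Let a ~ Bin(k, p) be DLTs among melanoma patients in the pool, b ~ Bin(5−k, p) among glioblastoma patients in the pool, and c ~ Bin(5−k, p) among later Cohort 1 patients. Both counts stay below two with probability

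P(both) = P(a=0)·P(b≤1)² + P(a=1)·P(b=0)²,

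since b and c have the same distribution. The chance that the pool passes while Cohort 1 has two or more DLTs is P(a+b≤1) − P(both).

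Example, k = 2, p = 30%: P(both) = 0.49 × 0.784² + 0.42 × 0.343² = 0.301 + 0.049 = 0.351. The disagreement probability is 0.528 − 0.351 = 0.178 (from unrounded values).

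| k | Pool passes, Cohort 1 has ≥2 DLTs: p = 10 / 20 / 30% | Both counts below two: p = 10 / 20 / 30% |
|---|---|---|
| 0 | 7.5 / 19.4 / 24.9% | 84.4 / 54.4 / 27.9% |
| 1 | 6.7 / 16.7 / 21.4% | 85.1 / 57.0 / 31.5% |
| 2 | 5.8 / 14.0 / 17.8% | 86.1 / 59.8 / 35.1% |
| 3 | 4.5 / 10.8 / 13.8% | 87.4 / 62.9 / 39.0% |
| 4 | 2.6 / 6.6 / 8.6% | 89.2 / 67.2 / 44.2% |
| 5 | 0 / 0 / 0% | 91.9 / 73.7 / 52.8% |

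The right-hand column matters only if both counts are meant to bind. Even then it equals the probability of moving to expansion only if expansion waits for Cohort 1 to finish, which 1.1 does not say.

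**Step 3: the common-rate assumption.** If the DLT rate were 30% in melanoma and 10% in glioblastoma, the pooled gate would pass with probability 92/86/78/70/61% for k = 0/1/2/3/4, rather than 53%.

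**Step 4: the word *successfully*.** Section 1.1 requires five pooled patients to have reached the end of the window successfully. Section 5.4.4 defines this as at least three vaccinations and no DLT. Taken literally, the gate becomes five DLT-free patients plus at most one with a DLT, that is, at most one DLT in up to six patients. P(0 or 1 of 6) is 88.6/65.5/42.0/23.3/10.9/4.1% at p = 10 to 60%, which is not the printed table.

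**Step 5: a separate small slip.** Section 14.1 says that above a 35% rate the chance of four or more DLTs in 10 is at least 50%. The exact value is 0.486 at 35%, crosses 0.5 at 35.5%, and is 0.513 at 36% (as the adjacent table prints).

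**The case against.** The best defence is that there is only one gate. The pooling paragraph in 1.1 is framed as the way safety is evaluated in the five-patient cohort of either trial, so it describes how the five are made up and does not add a second test. The 14.1 table speaks of five patients without saying that they have melanoma. This is the natural reading, and it stands: under a common rate the table and its 92% sentence are correct.

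A reader might infer from the right-hand column of the working table that the printed probabilities are wrong and the 92% assurance fails. The documents do not support that, because no passage says that both counts apply together.

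A reader might also infer that the later Cohort 1 patients are unprotected. That is not supported either. Taken literally, 5.4.1 and 14.1 still name every Cohort 1 patient. A patient whose grade 3 toxicity is a DLT is removed (6.3.1), and two grade 4 or greater attributable toxicities suspend the trial (6.3.3). The monitoring committee may receive DLT information (12.2), the external board reviews accumulated data for participant safety (12.3), and DLTs are listed by dose level (14.4). None of these, apart from the literal Cohort 1 rule, counts DLTs against a limit.

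Finally, the background points to low rates. Section 2.1.1 reports nothing above grade 2 in the cited long-peptide studies, and 2.1.2.4 reports no grade 3 or 4 events in the ovarian-cancer peptide and poly-ICLC trial. At a 5% rate the disagreement probability is only 2.1% to 0.8% for k = 1 to 4. That limits the practical size. It does not supply the missing sentence on what a second Cohort 1 DLT does after expansion has begun.

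**Conclusion.** The point holds as a gap between safety rules, not as an error in the table. Section 1.1 on one side and 5.4.1 and 14.1 on the other leave open whether the two-DLT rule continues for melanoma patients who complete Cohort 1 after the pooled gate opens and, if it does, what it triggers. The two harms belong to alternative readings and cannot both occur, but each reading leaves something unspecified.

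The chance of a pooled pass with two or more DLTs in this trial's first five falls from 7.5% to 2.6% as k goes from 0 to 4 at a 10% DLT rate, from 19% to 7% at 20%, and from 25% to 9% at 30%. It is zero at k = 5. These figures rest on equal DLT rates, independence and an unknown k. The finding that the rule is unspecified does not depend on them.

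**What to change.** 1. Reconcile 1.1, 5.4.1 and 14.1 on whether the Cohort 1 two-DLT rule continues after the pooled gate opens, which DLT count covers the melanoma patients treated afterwards, and what follows for expansion patients already on treatment. The choice is the sponsor's.
2. Reconcile *successfully* in 1.1 with its DLT-free definition in 5.4.4.
3. Label the 14.1 table with the gate it describes. If that gate is pooled, state the common-DLT-rate assumption.
4. Only if the sponsor decides that both counts bind, recompute the table and its summary sentences and say whether expansion waits for Cohort 1. For k = 0 to 4 the chance of meeting both would be 84–89% at a 10% rate (92 printed), 54–67% at 20% (74 printed) and 28–44% at 30% (53 printed).
5. Separately, in the expansion stopping paragraph of 14.1, replace the threshold of higher than 35% with 36% or higher.

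The cost is a few sentences and a table label, with no extra patients. The downside is that the stated operating characteristics may become less favourable if item 4 applies.
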